9.13.2 Classifications

Severity

The Investigator will evaluate the intensity of each adverse event using the following definitions:

- Mild: An event that is easily tolerated by the subject, causing minimal discomfort and not interfering with everyday activities (CTCAE Grade 1).
- Moderate: An event that is sufficiently discomforting to interfere with normal everyday activities (CTCAE Grade 2).
- Severe: An event that prevents normal everyday activities (CTCAE Grade 3-5).

Adverse events should be assessed according to the National Cancer Institute Common Terminology Criteria for Adverse Events (CTCAE) Version 4.0.

In the event of the occurrence of a severe adverse event, the Investigator will be instructed to immediately inform the sponsor for follow-up steps.

An AE that is assessed as severe should not be confused with an SAE. Severity is a category utilized for rating the intensity of an event; and both AEs and SAEs can be assessed as severe. An event is described as ‘serious’ when it meets one of the pre-defined outcomes as described in Section 9.13.1.

Causality

A blinded Investigator is obligated to assess the relationship between test drug and the occurrence of each AE/SAE. The Investigator will use clinical judgment to determine if there is a reasonable possibility that the pharmacological action of the test drug was responsible for the AE/SAE being reported. Alternative causes such as natural history of the underlying diseases, concomitant therapy, other risk factors, and the temporal relationship of the event to the test drug will be considered and investigated. The Investigator will also consult the Clinical Investigator’s Brochure and/or Product Information, for marketed products, in the determination of his/her assessment.

After careful medical consideration, the Investigator will evaluate the relationship of each adverse event to test drug applying the following definitions:

Probably Related – Good reasons and sufficient documentation to assume a causal relationship

Possibly related – A causal relationship is conceivable

Unlikely related – The event is most likely related to etiology other than the test drug

Not Related – Good reasons and sufficient documentation to exclude a causal relationship.

There may be situations when an SAE has occurred and the Investigator has minimal information to include in the initial report. However, it is very important that the Investigator always make an assessment of causality for every event prior to transmission of the SAE Report Form to the Sponsor (or designee).

9.13.3 Adverse Event Reporting

All events that meet the definition of an AE that occur in the period from when the patient has signed the informed consent form (ICF) through trial completion (final visit), or early termination, must be recorded on the adverse event eCRF. All SAEs will be recorded on the appropriate eCRF and on the Serious Adverse Event Report Form from the time written informed consent has been obtained through trial completion (final visit), or early termination.

At each contact between the investigative site and the patient (visit or phone), after the patient has had an opportunity to spontaneously mention any problems, the Investigator should inquire about the occurrence of AEs. The following are examples of open-ended questions that may be used to obtain this information:

“How are you feeling?”

“Have you had any medical problems since your last visit/assessment?”

“Have you taken any new medicines, other than those given to you in this study, since your last visit/assessment?”

All AEs and SAEs will be documented in source records (at each assessment time or when otherwise volunteered by the patient and recorded on the appropriate eCRF. Information to be collected includes the nature, date and time of onset, severity, duration, relationship to test drug, and outcome of the event. Even if the Investigator assesses the AE as not reasonably attributable to the test drug, its occurrence must be recorded in the source documents and reported on the eCRF along with the assessment of association.

The Investigator will treat the patient as medically required, and this may extend beyond the duration of the trial. The Investigator will record treatment and medications required to treat AEs on the appropriate eCRF(s). All SAEs, and any possibly/probably related severe AEs will be followed until resolution (no further changes in the event are expected, i.e., the point at which a subject experiencing such an AE is appropriately treated and stabilized even though they may continue to experience lingering sequelae that may never resolve.

DURECT will evaluate all AEs with respect to seriousness, causality and expectedness in accordance with Directive 2001/20/EC (3) and FDA Guidelines. The expectedness of an AE will be determined according to the current version of the Investigators Brochure.

9.13.3.1 Clinical Laboratory Assessments and Other Abnormal Assessments as Adverse Events and Serious Adverse Events

Abnormal clinical laboratory findings (e.g., clinical chemistry, hematology, and urinalysis) or other abnormal assessments (e.g., ECGs, vital signs) that are judged by the Investigator as clinically significant will be recorded as AEs or SAEs if they meet the definition described above. Abnormal assessments that are detected during the study or are present at baseline and significantly worsen following the start of the study will be reported as AEs or SAEs.

9.13.4 Reporting of Serious Adverse Events

Regardless of causality, the investigator must complete and submit an SAE form to PPD/CCI [REDACTED] within 24 hours of knowledge of the event for all serious adverse events.

PPD/CCI
[REDACTED]
[REDACTED]
[REDACTED]

The Investigator must indicate the SAE's relationship to test drug and sign the SAE form. When additional relevant information (final diagnosis, outcome, results of specific investigations, etc.) becomes available, the investigator must record that follow-up information in the eCRF. Follow-up information should be recorded according to the process used for reporting the initial event as described above. The investigator will follow all reportable events (i.e., SAEs) until resolution. Resolution means no further changes in the event would be expected, i.e., the point at which a subject experiencing such an AE is appropriately treated and stabilized even though they may continue to experience lingering non-serious sequelae that may never resolve.

PPD/CCI [REDACTED] will follow all SAEs until resolution (no further changes in the event are expected, i.e., the point at which a subject experiencing such an AE is appropriately treated and stabilized even though they may continue to experience lingering sequelae that may never resolve). PPD/CCI [REDACTED] will report all SAEs to DURECT within 1 business day of receipt.

All serious adverse events will also be reported on the AE CRF and concomitant medications administered in association with the serious AE will be documented on the CM CRF.

If a serious adverse event occurs and comes to the attention of the Investigator after trial completion/termination within 30 days of test drug dosing or within 30 days of the last trial visit (whichever occurs later), it must be reported immediately to PPD/CCI [REDACTED] in the same manner as the serious adverse events occurring during the trial. Investigators are not obligated to actively seek AEs from former study participants.

The Investigator must report SAEs to the IRB/IEC (per the IRB/IEC guidelines/SOPs), including all SAEs that have occurred at the investigative site and all trial related SAEs that have resulted in an expedited safety report to a regulatory agency. Concurrently, the Investigator must send DURECT documentation of such IRB/IEC notification or if reporting is not required immediately per IRB/IEC guidelines, then a copy of the local SOP stating the reporting guidelines should be supplied by the site to DURECT and the CRO.

DURECT complies with applicable regulatory requirement(s) related to the reporting of SUSARs to the competent authorities and the IRBs/IECs. In addition, DURECT will prepare annual safety reports covering all SUSARs that have occurred in clinical studies with the concerned test drug during the reporting period.

If a clinically relevant SAE related to PSC progression occurs, a blood sample (approximately 8 mL) will be collected as soon as possible for measurement of plasma DUR-928 concentration. The collection date and time should be documented. Refer to the sample processing, shipping and handling instructions provided within the laboratory manual.

9.13.5 Adverse Event Follow-up

During and after participation by a patient in a clinical trial, the Investigator will ensure that adequate medical care has been provided to the patient for any AEs including clinically significant laboratory values related to the trial. The Investigator will inform the patient when medical care will be needed for intercurrent illness(es) of which the Investigator becomes aware.

All SAEs and possibly/probably related, severe AEs must be followed by the Investigator until resolution (no further changes in the event are expected, i.e., the point at which a subject experiencing such an AE has been appropriately treated and stabilized even though they may continue to experience lingering sequelae that may never resolve), until the subject is lost to follow-up, or died and until all queries related to the AEs have been resolved. If a subject dies during participation in the study or during a recognized follow-up period, the Sponsor (or designee) must be notified immediately and then provided with a copy of any post-mortem findings, including histopathology.

9.14 Pregnancy

A urine pregnancy test (for female with childbearing potential) will be collected at screening visit, Day 1, Day 28 and Day 56 (end of study/early termination visit).

Female subjects will be advised to notify the Investigator immediately if they become pregnant during the course of the trial.

The Investigator must complete the appropriate pregnancy reporting forms and send them to DURECT (or DURECT's designee) within 14 calendar days of obtaining information of the pregnancy. The Investigator will follow the pregnancy through its course and complete the

appropriate documentation and forward immediately to DURECT (or DURECT's designee). The infant must be followed at least until one month of age. Consent of a parent must be obtained before registration of infant data.

Abortion, stillbirth and any malformation/disease must be reported as an SAE. A pregnancy outcome other than abortion, stillbirth and any malformation/disease as well as follow-up of the infant must be reported by the Investigator within 14 calendar days of obtaining the information using the appropriate pregnancy reporting forms.

10.0 PHARMACOKINETICS

At selected center(s), blood samples will be collected for drug concentration measurements in approximately 5 subjects from each dose group). These samples will be collected on Day 1 and Day 28 of dosing. ^{PPD/CCI} [REDACTED]

[REDACTED]

[REDACTED]

[REDACTED]

For details on sample collection please refer to [Appendix 2](#), for sample collection, processing and shipping details.

If a clinically relevant SAE related to PSC disease progression occurs, a blood sample (approximately 8 mL) will be collected as soon as possible for measurement of plasma DUR-928 concentration. The collection date and time should be documented, in addition to the date and time of last 2 doses taken. Refer to the sample processing, shipping and handling instructions provided within the laboratory manual.

11.0 STATISTICAL METHODS AND DATA ANALYSIS

11.1 Sample Size Determination

A sample size estimation was performed for the primary efficacy endpoint 'Percentage change from baseline to week 4 in the serum alkaline phosphatase (ALP) level.

Forty subjects will be randomized in total. Considering an early withdrawal rate of 10%, a sample size of 36 subjects (18 subjects per dose group) provides a statistical power of 80% to detect a 15% decrease (with a standard deviation of 35%) compared to baseline in serum ALP after 4 weeks of treatment using a one-group t-test. ^{PPD/CCI} [REDACTED]

[REDACTED]

Details of statistical measures and data analysis will be further specified in the Statistical Analysis Plan for this study.

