23. PPD/CCI

[figure not shown]

24. Any other clinically significant disorders or prior therapy that, in the opinion of the investigator, would make the subject unsuitable for the study or unable to comply with the dosing and protocol requirements

PPD/CCI

[figure not shown]
Pharmacokinetics: At selected center(s), blood samples will be collected for drug concentration measurements in approximately 5 subjects from each dose group. These samples will be collected on Day 1 and Day 28 of dosing. PPD/CCI

Plasma concentration data of DUR-928 from each available patient will be used to calculate relevant pharmacokinetic parameters determined using standard non-compartmental method with linear/log-trapezoidal rule utilizing an appropriate pharmacokinetic data analysis program.

Pharmacokinetic parameters for DUR-928 will be summarized using descriptive statistics.

PPD/CCI

Test drug, dosage and mode of administration: DUR-928 10 mg PO daily for 28 days
DUR-928 50 mg PO daily for 28 days

[figure not shown]
Comparator, dosage and mode of administration: N/A

Power Calculations: Forty subjects will be randomized in total. Considering an early withdrawal rate of 10%, a sample size of 36 subjects (18 subjects per dose group),^{PPD/CCI} [REDACTED] compared to baseline in serum ALP after 4 weeks of treatment using a one-group t-test. ^{PPD/CCI} [REDACTED]
[REDACTED]
[REDACTED]
(see [Section 11.1](#)).

Schedule of Events: Refer to [Table 1](#) below.

[figure not shown]
Table 1: Schedule of Events

PPD/CCI

Footnotes for Schedule of Events Table:

PPD/CCI

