7.3.1 Visit 1: Screening (Day -42 to Day 0)

All screening procedures will be performed after obtaining informed consent. After obtaining informed consent, subjects will be assigned a patient screening number and screening procedures will be performed. For the patient screening number, subjects will be numbered consecutively within each site in order of their consent into the trial. Only their assigned patient screening number and date of birth will identify subjects to the Sponsor in order to maintain anonymity.

Screening procedures include completion of:

- Demographic information
- Medical and surgical history
- Complete Physical examination (including height and weight)
- Vital signs (BP, HR, RR and T)
- Review of inclusion / exclusion criteria
- Safety laboratory tests (fasted: chemistry, hematology, urinalysis)
- sBA test, HIV-1, HIV-2, Hepatitis B, Hepatitis C and IgG4 (if absence of evidence of IgG4-related sclerosing cholangitis) testing
- Urine pregnancy test (females of childbearing potential)
- 12-lead ECG
- Record prior and concomitant medications (taken within 30 days of screening)
- Biomarker sample collection (see Section 9.6)
- VAS-itch score and 5-D pruritus itch scale diaries given to subjects for completion
- Transient Elastography/FibroScan® (only required if not performed within 3 months of screening)
- MRC or ERC (only required if not performed within 12 months of Day 1)
- Collection of partial Mayo score for IBD flare assessment

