7.3.2.2 Visit 2 - Randomization

After verification that patient meets entrance criteria (as noted in sections 5.3.2), the patient can be randomized to study treatment.

Subjects will be randomly assigned with equal allocation to one of two treatment groups.

- 10 mg DUR 928 administered for 28 days
- 50 mg DUR 928 administered for 28 days

Study drug administration ^{PPD/CCI} [REDACTED] :

F

[REDACTED]

C

[REDACTED]

- The subject will be sent home with enough study drug (7 days + 2 extra back up doses) to allow for daily dosing between study visits.

F

[REDACTED]

7.3.3

Treatment Period visits: Day 8^{PPD/CCI}, Day 15^{PPD/CCI}, Day 22^{PPD/CCI}
and Day 28^{PPD/CCI}

Subjects will return to clinic weekly for the following study procedures:

Day 8, 15 and 22^{PPD/CCI} :

- Vital signs (BP, HR, RR and T)
- Safety laboratory tests (fasted: chemistry, hematology, urinalysis)
- Biomarker sample collection
- Limited Physical exam (excluding height)
- sBA test (only on Day 15)
- Collection of unused drug and accountability check
- Concomitant medications
- Adverse events
- Dispensing of new drug supply (7 days + 2 extra back up doses)^{PPD/CCI}
- Transient Elastography/FibroScan® (only on Day 8 and Day 15)
- 12-Lead ECG
- Collection of partial Mayo score for IBD flare assessment

Day 28^{PPD/CCI}

- Vital signs (BP, HR, RR and T)
- Safety laboratory tests (fasted: chemistry, hematology, urinalysis)
- Biomarker sample collection
- sBA test
- PK samples (at selected sites)
- Collection of unused drug and accountability check
- Concomitant medications
- Adverse events
- Complete Physical exam (excluding height)
- 12-Lead ECG
- Transient Elastography/FibroScan®
- Collection of partial Mayo score for IBD flare assessment
- Urine Pregnancy Test for Females
- VAS-itch score and 5-D pruritus itch scale diaries given to subjects

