11.4 General Statistical Analysis Considerations

Study data will be summarized by treatment group and overall using descriptive statistics. Categorical variables will be reported with frequencies and percentages. Continuous variables will be reported with number of subjects, mean, standard deviation (SD), median, minimum, and maximum. 95% confidence intervals will also be provided when appropriate. All summaries, statistical analyses, and individual patient data listings will be completed using Version 9.3 or later of the SAS Statistical Analysis System (SAS Institute, Inc. Cary, NC).

The primary efficacy endpoint of detecting a signal with regards to the decrease of the percentage change from baseline in ALP will be tested in the ‘pooled group’ of both dose levels. The comparison between the dose levels will be performed by exploratory testing. Secondary and other endpoints will be analyzed and explored in a descriptive manner.

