11.6 Demographic and Baseline Characteristics

Demographic and baseline characteristics will be summarized using descriptive statistics specified in section 11.5. Baseline is defined as the last non-missing value before the first dose of study drug.

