11.7 Statistical Analyses of Efficacy Endpoints

11.7.1 Primary Efficacy Endpoint

- % change from baseline of serum ALP to the end of the study treatment
- % change from baseline of serum ALP at all post-baseline visits and throughout the follow-up period

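### Should the primary test of ALP use the log ratio instead of the percent change, because percent changes are skewed?

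*Combined protocol and SAP*

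**What the plan says.** The primary efficacy endpoint is a percent change. Section 11.7.1 lists the "change from baseline of serum ALP to the end of the study treatment", and also the percent change at every later visit. The test is named only in the sizing text (synopsis, Power Calculations, and Section 11.1), by the phrase "using a one-group t-test". With 36 evaluable subjects and 80% power, Section 11.1 aims to "detect a 15% decrease (with a standard deviation of 35%) compared to baseline in serum ALP after 4 weeks of treatment". Section 11.4 names no test. It describes the primary analysis as follows: "detecting a signal with regards to the decrease of the percentage change from baseline in ALP will be tested in the"; the sentence then refers to the two doses combined. Section 11.7.4 makes this the only confirmatory test.

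Alpha and sidedness are not visible; the text is redacted just after the t-test is named. Section 11.1 adds that "Details of statistical measures and data analysis will be further specified in the Statistical Analysis Plan for this study". No log scale appears in the visible text.

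Two other points bear on the matter. Section 11.6 states: "Baseline is defined as the last non-missing value before the first dose of study drug". Inclusion criterion 4 sets an ALP floor of 1.5 times ULN, with the rest of the criterion redacted. Chemistry, which includes ALP, is drawn at screening and again on Day 1. Randomization follows "After verification that patient meets entrance criteria".

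**The concern.** With no control arm, the trial's one confirmatory result depends on how a pre-to-post change behaves when the drug does nothing. Laboratory ratios are often closer to symmetric on the log scale. If so, random rises weigh more than random falls on the percent scale, and an inactive drug shows a mean change above zero. A one-sided test for a decrease would start at a handicap: it would reject less often than its nominal level and lose power. The reported mean would also lie above the typical subject's change. At stake is a missed signal in a small Phase 2 trial, for what looks like a one-line change of scale.

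**Working it through.** **1. The plan's own figure.** Inputs from Section 11.1: decrease 15%, SD 35%, n = 36. The standardized effect is 15/35 = 0.4286 and the noncentrality is 0.4286 × √36 = 2.571. From the noncentral t with 35 degrees of freedom, power is 81.0% at one-sided 5% and 70.6% at two-sided 5%. The stated 80% therefore fits one-sided 5%, which is an inference. The enrolment figure also fits: 36/0.9 = 40.

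**2. The handicap under an inactive drug.** Assume lognormal Day 28/baseline ratios with geometric mean 1 and an unselected baseline. If the percent change has standard deviation SD, the log variance v solves exp(v)(exp(v) − 1) = SD², and the mean percent change is exp(v/2) − 1. For SD 35%: exp(v) = (1 + √(1 + 4 × 0.35²))/2 = 1.110, so the log SD is 0.324 and the mean is √1.110 − 1 = +5.4%. Simulated rejection for a decrease (n = 36, one-sided 5%, 200,000 trials each):

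| SD with no effect | Mean % change | % change test | Log test |
|---|---|---|---|
| 20% | +1.9% | 1.8% | 5.0% |
| 25% | +2.9% | 1.4% | 5.0% |
| 30% | +4.1% | 1.1% | 5.0% |
| 35% | +5.4% | 0.9% | 5.0% |

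The effect is real under these conditions. The SD values are assumed, since the plan's 35% belongs to its treated alternative.

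**3. Power at the plan's target.** Keep the arithmetic mean at −15% and SD at 35%, and make the ratios lognormal. Then v = ln(1 + 0.35²/0.85²), the log SD is 0.396 and the geometric change is −21.4%. Power is 78% for percent change and 97% for the log test. The planned test delivers close to what was promised.

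A starker contrast appears if the target becomes a 15% geometric fall: 82.1% against 95.9% at SD 30%, and 65.9% against 90.6% at SD 35%. That target is smaller than the plan's. In arithmetic terms it is 0.85 × 1.041 − 1 = −11.5% and 0.85 × 1.054 − 1 = −10.4%. With the arithmetic change held at −15% and the same log SDs, the percent-change test has 96% and 90% power.

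**4. The result depends on the null.** If the arithmetic mean change is truly zero with lognormal ratios, the percent-change test is slightly liberal: 6.1% at log SD 0.20 and 7.0% at 0.324. The log test then rejects in 14.5% and 24.4%. If percent changes are symmetric (normal) with mean zero, the rates are about 5% for percent change and 12.6% (SD 20%) to 22.9% (SD 35%) for log.

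**5. The entry floor.** A floor selects subjects who are temporarily high, and their later values fall back without treatment. Assumptions: median ALP 2 to 3 times ULN before selection, between-person log SD 0.5 to 0.6, within-person log SD 0.324/√2 = 0.229, no true change, independent Day 28 fluctuation. Rounded false-positive rates (20,000 trials per case):

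| ALP value that must reach 1.5 × ULN | % change test | Log test |
|---|---|---|
| Screening only, Day 1 fluctuation independent | about 1% | about 5% |
| Screening only, screening/Day 1 correlation 0.5 | 1–2% | 7–11% |
| Screening only, correlation 0.8 | 2–4% | 9–17% |
| Screening and Day 1 | 2–4% | 8–14% |
| The baseline value alone | 2–7% | 10–23% |

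The log test holds its level only in the first row.

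**The case for a change.** The strongest argument for the log scale is point 3: with the plan's own target and SD, and lognormality as the only addition, power rises from 78% to 97%. Such a gain at no cost in subjects deserves to be taken seriously. It is also fair that alpha, sidedness, the test itself and the qualifying ALP sample cannot be read from the visible text, and that fixing the scale before data are seen matters in an open-label trial.

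The power gain stands if ratios are lognormal, but it comes with the exposure in points 4 and 5. One could make the log test primary only when baseline is a Day 1 sample separate from the qualifying value. That does not remove the problem: rows two and three of the last table have a separate Day 1 sample, and the log test still rejects in 7 to 17%. Nor does the text establish that Day 1 is free of selection, since Section 7.3.2.1 lists both the chemistry draw and the review of entry criteria before randomization. How quickly the central laboratory returns results is not stated.

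The missing details may lie in the redacted text or in the SAP to which Section 11.1 defers. A two-sided 5% test would indeed flag false rises (about 11% in total at SD 35% under the conditions of point 2), but Section 11.4 tests for a decrease and two-sided 5% does not reproduce the stated power.

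**Conclusion.** No change to the plan. The percent-change test is conservative, at about 1 to 2% against a nominal 5%, only if ratios are lognormal with geometric mean 1 and baseline is unselected. The documents give no ALP distribution and do not settle the selection. The planned test has 81.0% power as stated and about 78% under lognormality, so no visible figure is wrong. Moving the primary test to the log scale would replace the percent-change estimand with a geometric mean ratio and require a restated target. It would also make an uncontrolled trial more prone to a false claim of benefit whenever selection on ALP carries into the baseline value. This is a fair trade-off, and erring towards caution is defensible here.

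Presentation is partly covered already. Section 11.4 plans medians, and the 20%, 30% and 40% responder thresholds in Section 11.7.2 classify subjects identically on either scale. A supportive geometric mean change, and a description of the screening-to-Day 1 ratio to gauge regression to the mean, would be sensible optional additions. Neither would alter the confirmatory result.

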11.2 Patient Randomization

Subjects will be randomized into DUR-928 10 mg and 50 mg treatment groups at a 1:1 ratio, without stratification.

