11.3 Definition of Analysis Populations

Intent-to-Treat (ITT) Population: The ITT population will include all randomized subjects independent of their exposure to test drug.

Safety Population: The Safety population will include all subjects who received any amount of test drug. The Safety population will be used for all safety analyses.

Modified Intent-to-Treat (mITT) Population: The mITT population will include all randomized subjects who receive any test drug.

All efficacy endpoints will be analyzed using the mITT population. The disposition data will be summarized using ITT population.

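### Optional efficiency gain, not an error: the visible pooled one-group t-test has no dose term, and adding one costs almost no power and gains some if the two doses differ

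*Combined protocol and SAP*

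**What the plan says.** The only test named in the visible text is a one-group t-test, and it appears only in the two power statements. Section 11.1 gives the target as "a 15% decrease (with a standard deviation of 35%) compared to baseline in serum ALP after 4 weeks of treatment using a one-group t-test". The synopsis (Power Calculations) repeats "compared to baseline in serum ALP after 4 weeks of treatment using a one-group t-test". On numbers, Section 11.1 says: "Considering an early withdrawal rate of 10%, a sample size of 36 subjects (18 subjects per dose group) provides a statistical power of 80" per cent. Text after that sentence is redacted, and the section closes with "Details of statistical measures and data analysis will be further specified in the Statistical Analysis Plan for this study".

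On allocation, Section 11.2 says "Subjects will be randomized into DUR-928 10 mg and 50 mg treatment groups at a 1:1 ratio, without stratification". Section 11.3 adds "All efficacy endpoints will be analyzed using the mITT population", meaning everyone randomised and dosed. Section 11.4 says that "detecting a signal with regards to the decrease of the percentage change from baseline in ALP will be tested in the" two dose levels taken together, and then: "The comparison between the dose levels will be performed by exploratory testing". Section 11.4 also promises 95% confidence intervals, but only where appropriate. Section 11.7.4 makes the primary criterion the only confirmatory test. The synopsis lists no comparator.

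**The concern.** A one-group t-test on pooled data treats all subjects as one sample. If 10 mg and 50 mg have different true mean changes in ALP, that difference counts as random scatter and enlarges the standard error of the pooled mean. The randomised dose is known for every subject, so this part of the scatter can be removed for one degree of freedom.

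What is at stake is a little power, not validity. The design has almost no spare power: 36 is the smallest number that reaches 80% at one-sided 5%.

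A related reporting point concerns the dose contrast. With no control arm, the pooled change from baseline is an uncontrolled before-after comparison, and 50 mg minus 10 mg is the only comparison that randomisation protects. A bare exploratory p-value would convey little about it.

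**Working it through.** **Inputs from the documents.** Mean fall 15 points, SD 35%, 36 evaluable as 18+18, power 80%, 10% withdrawal (Section 11.1); 1:1 allocation (Section 11.2).

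**Assumptions.** Alpha is not visible; one-sided 5% is inferred below. The gap g between the dose means is not given; 10, 20 and 30 points are used. The text does not say whether 35% is a within-dose or a total SD, so both are run.

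**1. The plan's own figure.** Noncentrality = (15/35) × √36 = 2.571. With 35 df the one-sided 5% critical value is 1.690, and power from the noncentral t is 80.96%. The stated 80% reproduces. So does the randomised number: 36/0.9 = 40.

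**2. Dose-factor model, within-dose SD 35%.** The estimate is the arm-size-weighted mean of the two dose means, (n₁m₁ + n₂m₂)/(n₁ + n₂), which is identical to the pooled mean. The error is the within-dose SD on N − 2 = 34 df (critical value 1.691). Power is 80.92% whatever the gap, so the cost at gap 0 is 80.96 − 80.92 = 0.04 points.

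**3. Pooled t-test when the doses differ.** The scaled error sum of squares is noncentral chi-square with 35 df and λ = 36 × (g/2)²/35². Power comes from averaging the normal tail over that distribution.

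| Gap g | λ | Pooled t | Dose factor | Difference (points) |
|---|---|---|---|---|
| 0 | 0 | 80.96% | 80.92% | −0.04 |
| 5 | 0.18 | 80.84% | 80.92% | +0.08 |
| 10 | 0.73 | 80.48% | 80.92% | +0.44 |
| 20 | 2.94 | 79.03% | 80.92% | +1.89 |
| 30 | 6.61 | 76.58% | 80.92% | +4.34 |

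The two methods break even at a gap of 2.9 points.

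**4. If 35% is the total SD.** The within-dose SD is then √(35² − (g/2)²), that is 34.6, 33.5 and 31.6 at gaps 10, 20 and 30. Pooled versus dose factor: 81.2% vs 81.6%, 81.9% vs 83.8%, 83.2% vs 87.4%. The gains are similar, but pooled power never falls below 80%.

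**5. Other numbers analysed** (within-dose SD 35%).
- All 40 evaluable: cost 0.03 points; gains 0.39, 1.66 and 3.83.
- 20 on 10 mg and 16 on 50 mg, with the larger fall on 50 mg: gains 0.47, 2.1 and 5.1.
- The reverse split, 16 and 20: gains 0.40, 1.6 and 3.3.
- At both unequal splits the cost at gap 0 stays 0.04 points.

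**6. The dose contrast.** SE = 35 × √(2/18) = 11.67. With 34 df the 95% half-width is 2.032 × 11.67 = 23.7 points, unadjusted. A two-sided 5% test has 13%, 38% and 70% power at gaps of 10, 20 and 30. If baseline log ALP correlated 0.3 or 0.5 with percentage change (assumed values), the half-width would fall to 22.6 or 20.6.

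**The case against.** The case against acting has five parts.

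- **Nothing is wrong as planned.** Pooling is declared, the test is valid and the stated power reproduces. This stands, and it is why the point is optional.
- **The gain is small unless the doses differ widely.** With an equal split and a mean fall of 15, a gap of 20 means falls of 5 and 25, and a gap of 30 means one dose does nothing. Nothing visible supports gaps of that size. At a gap of 10 the gain is 0.44 points, whereas one extra subject (37 instead of 36) gives 81.9%. Below 2.9 points the change loses a trivial amount. This stands too.
- **35% is more naturally the SD of the single tested group.** A reader might infer from the within-dose figures that the trial is underpowered as planned. The documents do not support that: on the total-SD reading pooled power stays above 80%, and even on the within-dose reading it holds at 80% up to a gap of about 14 points.
- **The dose term may already be planned.** The t-test is named only in the power statements, text after the power sentence is redacted, and details are left to the SAP. The recommendation has to be conditional on this.
- **The dose contrast is already planned, with intervals where appropriate.** This is largely true. What remains is to commit to the interval and the baseline adjustment. The benefit of adjustment depends on a correlation that the documents do not give.

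A reader might also infer a power error, because a two-sided 5% test with 36 subjects would have only about 71%. That is not supported: alpha is not visible, and one-sided 5% reproduces the stated figure.

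**Conclusion.** This is a low-severity, optional efficiency improvement. As far as the text can be read, the primary test ignores the randomised dose. Including it leaves the tested mean unchanged, costs 0.04 points of power if the doses act equally, and gains about 0.4, 1.9 and 4.3 points at gaps of 10, 20 and 30.

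These figures rest on an inferred one-sided 5%, an 18+18 split, a within-dose SD of 35% and assumed gaps. Reading 35% as the total SD changes the gains little.

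A reader might go further and infer that the pooled test is invalid or that its error rate is wrong. It is not invalid. If neither dose changes ALP, its type I error is exactly the nominal level under the t-test's usual assumptions. It falls below nominal only if the doses have opposite effects that average to zero.

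**What to change.** Unless the redacted text or the SAP already provides for it, write two items into the SAP before the data are analysed:

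1. Test the primary hypothesis as the arm-size-weighted mean of the two dose means against zero, from a linear model for percentage change in ALP with dose as a factor (within-dose error, N − 2 df). State the weights in advance. Arm-size weights reproduce the pooled mean at any split, so the quantity that Section 11.4 tests is unchanged. Equal weights would target a different mean when the arms are unequal and the doses differ.
2. Report the exploratory 50 mg minus 10 mg difference with its 95% confidence interval, adjusted for baseline log ALP, and label it the only randomised comparison.

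The cost is SAP wording only. ALP is already measured at baseline, so no new data, visits or subjects are needed. The primary test gives up one degree of freedom, which is the 0.04 points shown above; the baseline adjustment takes one more from the exploratory contrast.
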